5.5 Participant Replacement Strategy

If a participant withdraws from the study, a replacement participant may be enrolled if deemed appropriate by the investigator and Sponsor. The replacement participant will generally receive the same intervention or intervention sequence (as appropriate) as the participant being replaced. The replacement participant will be assigned a unique treatment/randomization number.

6 STUDY INTERVENTION

Study intervention is defined as any investigational intervention(s), marketed product(s), placebo, or medical device(s) intended to be administered to a study participant according to the study protocol.

Clinical supplies study intervention(s) provided by the Sponsor will be packaged to support enrollment and replacement participants as required. When a replacement participant is required, the Sponsor or designee needs to be contacted before dosing the replacement participant. Clinical supplies will be affixed with a clinical label in accordance with regulatory requirements.

6.1 Study Intervention(s) Administered

The study intervention(s) to be used in this study are outlined in [Table 2](#).

Country-specific requirements are noted in Appendix 7.

Table 2 Study Interventions

Arm Name	Arm Type	Intervention Name	Intervention Type	Dose Formulation	Unit Dose Strength(s)	Dosage Level(s)	Route of Administration	Regimen	Use	IMP or NIMP/AxMP	Sourcing
MK-2060	Experimental	MK-2060	Drug	Lyophilized Powder	CCI [REDACTED]	50 mg	IV Infusion	Single 60-minutes infusion	Test Product	IMP	Provided centrally by the Sponsor
Placebo	Placebo Comparator	Placebo	Drug	Sterile Solution	Saline	0 mg	IV Infusion	Single 60-minutes infusion	Placebo	IMP	Provided centrally by the Sponsor
The classification of IMP and NIMP/AxMP in this table is based on guidance issued by the European Commission and applies to countries in the EEA. Country differences with respect to the definition/classification of IMP and NIMP/AxMP may exist. In these circumstances, local legislation is followed.											
The normal saline provided by the Sponsor as placebo should be used to reconstitute MK-2060.											
Normal saline = 0.9% Sodium Chloride Injection											

All supplies indicated in **Table 2** will be provided per the “Sourcing” column depending on local country operational requirements. If local sourcing, every attempt should be made to source these supplies from a single lot/batch number where possible (eg, not applicable in the case where multiple lots or batches may be required due to the length of the study, etc).

Refer to Section 8.1.8 for details regarding administration of the study intervention.

6.2 Preparation/Handling/Storage/Accountability

6.2.1 Dose Preparation

Specific calculations or evaluations required to be performed to administer the proper dose to each participant are outlined in a separate document provided by the Sponsor. The rationale for selection of doses to be used in this study is in Section 4.3.

6.2.2 Handling, Storage, and Accountability

The investigator or designee must confirm appropriate temperature conditions have been maintained during transit for all study intervention received, and any discrepancies are reported and resolved before use of the study intervention.

Only participants enrolled in the study may receive study intervention, and only authorized site staff may supply or administer study intervention. All study interventions must be stored in a secure, environmentally controlled, and monitored (manual or automated) area in accordance with the labeled storage conditions with access limited to the investigator and authorized site staff.

The investigator, institution, or the head of the medical institution (where applicable) is responsible for study intervention accountability, reconciliation, and record maintenance (ie, receipt, reconciliation, and final disposition records).

For all study sites, the local country Sponsor personnel or designee will provide appropriate documentation that must be completed for drug accountability and return, or local discard and destruction if appropriate. Where local discard and destruction is appropriate, the investigator is responsible for ensuring that a local discard/destruction procedure is documented.

The study site is responsible for recording the lot number, manufacturer, and expiry date for any locally purchased product (if applicable) as per local guidelines unless otherwise instructed by the Sponsor.

The investigator shall take responsibility for and shall take all steps to maintain appropriate records and ensure appropriate supply, storage, handling, distribution, and usage of study interventions in accordance with the protocol and any applicable laws and regulations.

6.3 Measures to Minimize Bias: Randomization and Blinding

6.3.1 Intervention Assignment

Participants will be assigned randomly according to a computer-generated allocation schedule.

A sample allocation schedule is shown in [Table 3](#).

Table 3 Sample Allocation Schedule

N ^a	Dose
CC L	MK-2060 50 mg
C C	Placebo

^a Japanese older participants with ESRD on HD or HDF. Approximately up to 16 participants will be randomized and a minimum of approximately 8 HDF participants should be included.

Placebo: 0.9% sodium chloride infusion

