1.2 Schema

The study design is depicted in [Figure 1](#) and [Table 1](#).

Figure 1 Study Schema

- * Screening 1 should occur within 28 days prior to intervention randomization.
- Screening 2 should occur within 5 to 8 days prior to intervention randomization.
- Screening 2 should occur after review of all data from Screening 1.
- Dialysis should be done at Screenings 1 and 2.

Table 1 Study Schema

N ^a	Dose ^{b, c}
CCI	MK-2060 50 mg
	Placebo

^a Japanese older participants with ESRD on HD or HDF. Approximately up to 16 participants will be randomized and a minimum of approximately CCI participants should be included.

^b Dosing in this study will be initiated after CCI of safety data from the highest IV dose in MK-2060-013 has been reviewed. Available safety, PK and/or PD data in other MK-2060 clinical studies might also be reviewed prior to initiate dosing in this study.

^c The suggested doses may be adjusted downward based on newly available safety, PK and/or PD data observed in MK-2060-013 and/or in other MK-2060 clinical studies.

Placebo: 0.9% sodium chloride infusion

MK-2060-013: Single Dose Study of MK-2060 in Healthy Japanese Participants

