4 STUDY DESIGN

4.1 Overall Design

This is a randomized, placebo-controlled, parallel-group, multi-site, double-blind study of MK-2060 in Japanese older participants with ESRD on dialysis. The study will evaluate the safety, tolerability, PK and PD of a single dose IV administration of MK-2060 in Japanese older participants with ESRD on dialysis (participants assigned male sex at birth or WONCBP between the age of 50 to 80 years).

The study design is depicted in [Figure 1](#) and [Table 1](#).

Approximately up to 16 participants will be randomized in a ratio of [CCI](#) and receive a single dose of MK-2060 or placebo (0.9% sodium chloride infusion). All participants will be domiciled until approximately [CCI](#) hours postdose (completion of dialysis on Day [CCI](#)). Blood samples for PK, PD and ADA assay will be obtained predose and at selected time points up to 150 days postdose. All participants will be closely monitored for safety and tolerability for approximately 164 days.

Because this is a Phase 1 assessment of MK-2060 in humans, the PK, pharmacodynamic, and safety profiles of the compound are still being elucidated. This protocol is therefore written with flexibility to accommodate the inherent dynamic nature of Phase 1 clinical studies. Refer to Section 8.11.6 for examples of modifications permitted within the protocol parameters.

Specific procedures to be performed during the study, including prescribed times and associated visit windows, are outlined in Section 1.3 of the SoA. Details of each procedure are provided in Section 8.

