4.2 Scientific Rationale for Study Design

MK-2060 is being developed for the prevention of thrombotic vascular events in ESRD patients, thus the objectives of this study are to evaluate safety, tolerability, PK, and PD of MK-2060 after a single dose IV administration in Japanese patient population [older participants with ESRD on dialysis (participants assigned male sex at birth or WONCBP

between the age of 50 to 80 years)]. Approximately up to 16 participants with ESRD on dialysis who meet study eligibility criteria may be enrolled in this study.

Dialysis modality in this study includes HD and HDF. The Japanese patients treated by HDF have been increasing in number rapidly since 2012. HD and HDF accounted for 49.3% and 47.1% of all dialysis patients, respectively in 2020 [JSDT Renal Data Registry 2020]. Therefore, this study will enroll both HD and HDF participants. Since only HD participants were enrolled in MK-2060-004 (Phase 1 study in non-Japanese participants), this study will mainly enroll HD participants and a minimum of approximately [REDACTED] HDF participants will be enrolled. [REDACTED]

[REDACTED] is not removed by both HD and HDF, it is anticipated that there is no PK difference between HD and HDF patients.

The mean age of prevalent dialysis patients in Japan was 69.40 years, indicating a gradual annual increase. The age group of 70 to 74 had the highest percentage both in males and females [JSDT Renal Data Registry 2020]. The mean age of HD and HDF patients was 70.00 years and 67.21 years, respectively. The mean dialysis vintage of HD patient was 6.99 years and 50.7% was less than 5 years of dialysis vintage. On the other hand, the mean dialysis vintage of HDF patient was 8.44 years and 40.9% was less than 5 years of dialysis vintage. HDF is applied to relatively young patients with a longer dialysis vintage than HD in 2018 [JSDT Renal Data Registry 2018]. Therefore, this study is being conducted in older participants ages from 50 years to 80 years.

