6.3.2 Stratification

No stratification based on age, sex, or other characteristics will be used in this study.

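### Does a minimum of about 8 HDF participants in about 16 contradict a mainly-HD study, and should randomisation be stratified by dialysis modality?

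*Combined protocol and SAP*

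**What the plan says.** - **Section 4.2** explains that MK-2060-004 enrolled only HD participants and so "this study will mainly enroll HD participants and a minimum of approximately" some number of HDF participants will be included; the number is blacked out. The same section reports that "HD and HDF accounted for 49.3% and 47.1% of all dialysis patients, respectively in 2020", and that "it is anticipated that there is no PK difference between HD and HDF patients".
- **Section 1.2, Table 1 footnote** carries the minimum with its figure redacted: "Approximately up to 16 participants will be randomized and a minimum of approximately CCI participants should be included".
- **Section 6.3.1, Table 3 footnote** is the only place where a figure can be read: "Approximately up to 16 participants will be randomized and a minimum of approximately 8 HDF participants should be included".
- **Section 6.3.2**: "No stratification based on age, sex, or other characteristics will be used in this study".
- **Section 4.1** gives the allocation ratio, but it is blacked out.
- **Sections 9.3, 9.6, 9.8 and 9.9** contain no hypotheses, no power calculation and no analysis by modality. The primary endpoint is adverse events (Section 9.4).

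**The concern.** Two things look wrong.

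First, a floor of 8 HDF under a ceiling of 16, with no legible cap on HDF, leaves HD with half the study at best. The stated reason for favouring HD is comparability with the non-Japanese HD data from MK-2060-004. A site could follow Table 3 exactly and still not deliver that mix.

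Second, the plan sets a quota for modality and then randomises without regard to it. In a study this small the HDF share could differ noticeably between MK-2060 and placebo. If modality affected the outcomes, the aPTT ratio (MK-2060 to placebo) and the hemostasis comparison would carry that difference. The expectation of no HD/HDF difference in PK could be examined only if both modalities were present on MK-2060.

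**Working it through.** **Inputs.** Total of about 16 and HDF minimum of about 8 (Table 3 footnote). The allocation ratio is redacted, so 12:4, 10:6 and 8:8 (MK-2060:placebo) are assumed. Neither the 16 nor the 8 has a stated derivation, so there is no plan figure to reproduce.

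**Step 1: the HD share.** The HD maximum is N minus the HDF minimum.
- 16 − 8 = 8, or 8/16 = 50%.
- If enrolment stops at 14: 14 − 8 = 6, or 6/14 = 43%.
- One participant of slack either way: 16 − 7 = 9, or 9/16 = 56%; 17 − 8 = 9, or 9/17 = 53%.

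The literal reading gives an even split, and the approximate wording allows a narrow HD majority. By the Section 4.2 registry figures, HDF is 47.1/(47.1 + 49.3) = 48.9% of HD and HDF patients combined, so an even split would also be close to the treated population.

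**Step 2: chance imbalance.** Take 8 HDF and 8 HD. With n on placebo, the number k of HDF participants on placebo is hypergeometric: P(k) = C(8,k)·C(8,n−k)/C(16,n). The gap in HDF share is |k/n − (8−k)/(16−n)|.

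| Ratio | P(exact balance) | P(any imbalance) | Smallest non-zero gap | P(gap ≥ 50 points) | P(placebo one modality) | Fewest of either modality on MK-2060 |
|---|---|---|---|---|---|---|
| 12:4 | 784/1820 = 43.1% | 56.9% | 33 points | 7.7% | 140/1820 = 7.7% | 8 − 4 = 4 |
| 10:6 | 3136/8008 = 39.2% | 60.8% | 27 points | 11.9% | 56/8008 = 0.7% | 8 − 6 = 2 |
| 8:8 | 4900/12870 = 38.1% | 61.9% | 25 points | 13.2% | 2/12870 = 0.016% | 0, with probability 0.016% |

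A threshold of 25 points therefore counts every allocation that is not perfectly balanced, including those one participant away. The 57% to 62% is not a rate of serious imbalance; gaps of 50 points or more occur in 8% to 13%.

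**Step 3: the PK check.** Only MK-2060 participants contribute MK-2060 PK. The last column shows that both modalities are certain to be present on MK-2060 at 12:4 and 10:6, and all but certain at 8:8. A single-modality placebo group has no bearing on PK.

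**Step 4: aPTT and hemostasis.** aPTT is analysed as log fold-change from the participant's own baseline (Sections 9.4 and 9.6). Time to hemostasis has a baseline averaged over two screening sessions (Section 8.3.3) and is to be assessed as change from it (Section 4.2.1.1). Stable differences between HD and HDF patients cancel. For modality to move the aPTT ratio, it must change the fold-change itself. If it multiplies fold-change by r in both arms, a gap g multiplies the ratio by r^g. One participant away from balance gives g = 1/3 at 12:4 and 1/4 at 8:8, and r = 1 gives no shift. The documents offer no evidence that r differs from 1. Over repeated randomisation the shift averages to zero, so it is random error and not bias.

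**The case for a change.** The best opposing case has four parts.

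1. **If the 8 is real, the two sections pull in different directions**, and a bare 56% HD majority is a weak reading of mainly. This stands as a wording point. The figure may well be real: Section 9.1 shows an aPTT threshold of 1.5 that Section 9.6 blacks out, so the redaction is not uniform. It may also be a misread box, since the neighbouring cells of Table 3 are broken redactions. The public text cannot settle this. Section 4.2 also has blacked-out text just after the HDF minimum.

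2. **The no-difference expectation concerns PK, not aPTT or hemostasis**, and Section 4.2 reports that HD and HDF patients differ in mean age (70.00 against 67.21 years) and dialysis vintage (6.99 against 8.44 years). True, but these are stable characteristics that the within-participant baseline largely absorbs.

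3. **A smaller true minimum could worsen imbalance.** With an assumed 4 HDF of 16, placebo has none in C(12,4)/C(16,4) = 495/1820 = 27% of allocations at 12:4, 210/1820 = 11.5% at 10:6 and 70/1820 = 3.8% at 8:8. That is correct. The MK-2060 arm, however, would lack HDF in only 1/1820 = 0.05%, 15/1820 = 0.8% and 70/1820 = 3.8%.

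4. **Stratifying is cheap**, because a registration center assigns numbers after eligibility is confirmed (Section 8.1.8.1). The cost is small, but so is the gain: no planned model or summary uses modality, and short lists risk incomplete blocks that shift the overall ratio by a participant.

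**Conclusion.** No change to the plan is needed. The apparent contradiction depends on one legible digit among redactions and disappears with a shift of one participant, which the approximate wording permits. If the sponsor's unredacted text confirms 8, Section 4.2 and the footnotes to Tables 1 and 3 deserve a clerical reconciliation. No sample size, power, error rate or planned result depends on it.

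Randomising without stratification is an openly stated choice and a reasonable one here. Exact modality balance would be missed in 57% to 62% of allocations and a gap of 50 points or more would arise in 8% to 13%, but both modalities remain on MK-2060 and the PD comparisons use each participant's own baseline. Individual PK values are already to be listed (Section 9.1) and modality is established at eligibility (Section 5.1), so an analyst can summarise PK and aPTT by modality if wanted; that is optional.

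The conclusion rests on assumed ratios between 12:4 and 8:8, on 8 HDF of 16 for the main figures, and on modality having no material effect on change after dosing, which the documents give no reason to doubt.

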6.3.2 Stratification

No stratification based on age, sex, or other characteristics will be used in this study.

6.3.3 Blinding

A double-blinding technique will be used. MK-2060 and placebo will be prepared and/or dispensed in a blinded fashion by an unblinded pharmacist or qualified study-site personnel. The participant, the investigator, and Sponsor personnel or delegate(s) who are involved in the study intervention administration or clinical evaluation of the participants are unaware of the intervention assignments.

See Section 8.1.10 for a description of the method of unblinding a participant during the study should such action be warranted.

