2.1 Study Rationale

The purpose of this study is to assess the safety, tolerability, PK and PD of MK-2060 after a single dose IV administration in Japanese older participants with ESRD on dialysis. Data from this study etc. will be used to aid dose selection of MK-2060 in Japanese participants in future studies.

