4.2.2 Rationale for the Use of Placebo

The primary goal of the study is to evaluate the safety and tolerability of MK-2060 in Japanese older participants with ESRD on dialysis. A placebo-controlled study will allow for an unbiased assessment of safety and tolerability of MK-2060. Secondary and exploratory outcomes are also supported by the use of placebo, including evaluation of the effect of MK-

2060 on aPTT following single IV dose, which should only be observed in participants with active treatment.

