9.5 Analysis Populations

The following populations are defined for the analysis and reporting of data. All participants will be reported, and their data analyzed, according to the treatment(s) they actually received.

All Participants as Treated (APaT): The All Participants as Treated Population consists of all participants who received at least one dose of treatment. This population will be used for assessments of safety.

Per-Protocol (PP): The Per-Protocol Population consists of the set of data generated by the subset of participants who comply with the protocol sufficiently to ensure that these data will be likely to exhibit the effects of treatment, according to the underlying scientific model. Compliance covers such considerations as exposure to treatment, availability of measurements and absence of major protocol deviations. Major protocol deviations will be identified to the extent possible prior to unblinding by individuals responsible for data collection, and its analysis and interpretation. Any participants or data values excluded from analysis will be identified, along with their reason for exclusion, in the CSR. At the end of the study, all participants who are compliant with the study procedure as aforementioned and have available data from at least one treatment will be included in the Per-Protocol dataset. This population will be used for the PK and PD analyses.

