10.1.7 Data Quality Assurance

All participant data relating to the study will be recorded on printed or electronic CRF unless transmitted to the Sponsor or designee electronically (eg, laboratory data). The investigator or qualified designee is responsible for verifying that data entries are accurate and correct by physically or electronically signing the CRF.

Detailed information regarding Data Management procedures for this protocol will be provided separately.

The investigator must maintain accurate documentation (source data) that supports the information entered in the CRF.

The investigator must permit study-related monitoring, audits, IRB/IEC review, and regulatory agency inspections and provide direct access to source data documents.

Study documentation will be promptly and fully disclosed to the Sponsor by the investigator upon request and also shall be made available at the study site upon request for inspection, copying, review, and audit at reasonable times by representatives of the Sponsor or any regulatory authorities. The investigator agrees to promptly take any reasonable steps that are requested by the Sponsor or any regulatory authorities as a result of an audit or inspection to cure deficiencies in the study documentation and worksheets/CRFs.

The Sponsor or designee is responsible for the data management of this study including quality checking of the data.

Study monitors will perform ongoing source data review and verification to confirm that data entered into the CRF by authorized site personnel are accurate, complete, and verifiable from source documents; that the safety and rights of participants are being protected; and that the study is being conducted in accordance with the currently approved protocol and any other study agreements, ICH GCP, and all applicable regulatory requirements.

Records and documents, including participants' documented informed consent, pertaining to the conduct of this study must be retained by the investigator for 15 years after study completion unless local regulations or institutional policies require a longer retention period. No records may be destroyed during the retention period without the written approval of the Sponsor. No records may be transferred to another location or party without written notification to the Sponsor.

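### Does visible postdose safety aPTT, with a loosely defined Per-Protocol set, undermine the blind and the aPTT estimates?

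*Combined protocol and SAP*

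**What the plan says.** - **Blinding.** Section 6.3.3 treats participants and the investigator as blinded, and says that "Sponsor personnel or delegate(s) who are involved in the study intervention administration or clinical evaluation of the participants are unaware of the intervention assignments". Section 4.2.2 adds: "A placebo-controlled study will allow for an unbiased assessment of safety and tolerability of MK-2060". The same paragraph says an aPTT effect is expected on active treatment only.
- **Safety aPTT.** Section 8.7 has postdose aPTT and PT run by the central laboratory for safety, separately from the PD vendor whose values feed the statistical analysis. Section 8.3.7 and Appendix 2 require review of the safety laboratory reports. Sections 6.6.1 and 8.1.11 attach actions to aPTT fold-changes. Appendix 8 counts nine safety aPTT/PT draws in the treatment period.
- **Per-Protocol set.** Section 9.5 defines it through "participants who comply with the protocol sufficiently to ensure that these data will be likely to exhibit the effects of treatment", with exposure, availability of measurements and absence of major deviations as considerations. "Major protocol deviations will be identified to the extent possible prior to unblinding by individuals responsible for data collection, and its analysis and interpretation". Excluded participants or values must be identified with reasons in the CSR. "This population will be used for the PK and PD analyses".
- **Analyses.** Section 9.6 plans a mixed model on log fold-change in aPTT, with a geometric mean ratio (GMR) and 90% CI by time, and a responder proportion at 168 hours (threshold 1.5-fold in Section 9.1). Safety analyses use all treated participants.
- **Use.** Section 2.1: "Data from this study etc. will be used to aid dose selection of MK-2060 in Japanese participants in future studies".

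**The concern.** Two issues meet here.

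First, an investigator who sees a clearly prolonged aPTT from a sample free of heparin may infer the arm, and the same investigator rates AE intensity and causality. Sections 6.3.3 and 4.2.2 do not mention this.

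Second, safety aPTT measures the same variable as the secondary PD endpoint, in another laboratory. Section 10.1.7 says data go on the CRF "unless transmitted to the Sponsor or designee electronically (eg, laboratory data"), and nothing visible withholds aPTT from those who decide on exclusions. With no itemised list of major deviations, and no planned repeat of the PD aPTT model or the 168-hour proportion in all treated participants, a result-driven exclusion could move the estimate without any planned output isolating its effect. With about 16 participants, one exclusion is not trivial, and the data will inform dose selection. No hypotheses are prespecified (Section 9.8), so the stake is bias in an estimate, not an error rate.

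**Working it through.** The plan states no figure for this point, so there is none to reproduce. Total N is about 16 (Section 9.9). The allocation is redacted and no SD is given, so both are assumed below.

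**1. Could aPTT reveal the arm?** Section 6.6.1 gives 31.8 to 36.4 s for normal plasma and 99.5 to 128.1 s for FXI-deficient plasma. The smallest ratio is 99.5/36.4 = 2.73, so the ranges do not overlap. For a true fold-change f and log-SD s (equal in both arms), the chance that a random active value exceeds a random placebo value is Φ(ln f / (s√2)):
- f = 1.5: s = 0.10 gives 0.998; s = 0.25 gives 0.874.
- f = 2.0: s = 0.25 gives Φ(0.693/0.354) = 0.975.

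Partial inference is therefore plausible once a heparin-free result is reported. In heparin users that excludes the 1-hour sample; Section 6.6.1 takes 12 hours as their first usable time point.

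**2. How far could one exclusion move the GMR?** Assume normal log values with equal variance. Removing the extreme member of an arm of n shifts that arm's mean by E[max of n]/(n−1) SD:
- n = 8: 1.4236/7 = 0.203
- n = 12: 1.6292/11 = 0.148
- n = 4: 1.0294/3 = 0.343

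The 90% CI half-width at one time point is 1.7613·√(1/n₁+1/n₂), with t on 14 df: 0.881 SD for 8/8 and 1.017 SD for 12/4.

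| Exclusion | Shift in log-GMR (SD) | Share of half-width | GMR change, s = 0.10 to 0.30 |
|---|---|---|---|
| 8/8, lowest active or highest placebo | +0.203 | 23.1% | +2.1% to +6.3% |
| 12/4, lowest active | +0.148 | 14.6% | +1.5% to +4.5% |
| 12/4, highest placebo | +0.343 | 33.7% | +3.5% to +10.8% |

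If the choice is made on the safety-laboratory value and that correlates 0.5 to 0.9 with the PD-vendor value (assumed), the shares fall to between 7% and 30%.

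**3. Which way would a choice made without knowing the arm push?** If the arms separate, the lowest value among all 16 is usually a placebo value. Removing it raises the placebo mean and lowers the log-GMR by 0.203 SD (8/8) or 0.343 SD (12/4). The highest value is usually active; removing it lowers the log-GMR by 0.203 or 0.148 SD. Discarding outlying aPTT values blind to arm therefore pulls the ratio towards 1. The upward shifts in the table need someone to infer the arm and then act on the result.

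**4. Responder proportion (illustrative).** Dropping one non-responder moves 6/8 to 6/7 (75% to 86%) or 9/12 to 9/11 (75% to 82%). Both counts would remain recoverable from the CSR listing of exclusions together with the individual data.

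**5. What room is there for discretionary exclusion?** There is one infusion. Section 6.4 has its start and end times recorded, and dose and identity confirmed by a second staff member. Sampling windows are fixed in Table 6. Discontinuation after dosing is not possible (Section 7.1). aPTT is a listed safety test in Table 8, so a descriptive all-treated summary of safety-laboratory aPTT falls within Section 9.6, subject to clinical judgement.

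**The case for a change.** The strongest case for a change is that the remedy is cheap: a deviation list that uses no results, one repeat of a model already programmed, and one sentence on blinding. Such a list protects fully only if it is written before results are seen. The CSR shows who was excluded but not how far the estimate moved. The all-treated safety summary is optional, uses another laboratory and fits no model, so it cannot stand in for a repeat of the PD analysis.

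Much of this stands as fact. No itemised list is given, Per-Protocol is the only population named for PD, and no all-treated repeat of the PD model is planned. It does not amount to a flaw:

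- Section 6.3.3 speaks of awareness of assignments; seeing a laboratory value is not a code break. Section 4.2.2 itself says the effect should appear only on active drug, so the possibility of inference is in plain view. The causality guidance in Appendix 3 even counts an expected pharmacologic effect as evidence of exposure. Masking aPTT would conflict with the monitoring in Sections 6.6.1 and 8.1.11, and a disclosure sentence would leave ratings and results as they are.
- AE counts are less exposed than ratings: all events after randomisation are reported (Section 8.4.1), open-ended questioning is preferred (Section 8.4.2), and the analysis is in all treated participants.
- The Per-Protocol sentence is about compliance. Reading only its closing words makes it sound based on outcome.
- Access to aPTT by those who decide on exclusions is inferred from silence. Section 10.1.7 is general CRF text and leaves data management procedures to a separate document.
- A ban on every MK-2060 result in deviation criteria would also bar assay evidence of a dosing or allocation error, which bears on exposure.

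**Conclusion.** No change to the plan follows. The blinding point is a fair trade-off between safety access and full masking of AE ratings. Its size cannot be stated, because the expected aPTT change, its variability and the allocation are redacted or not given. The Per-Protocol point is missing detail that analysts can fill sensibly: apply the compliance headings before unblinding, report exclusions as Section 9.5 requires and, if anyone is excluded, show the aPTT result with that participant included. If nobody is excluded, the two analyses coincide.

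The range of 15% to 34% of the CI half-width is a worst case for one deliberate exclusion at one time point. It rests on assumed splits of 8/8 to 12/4, normality and equal variances; a smaller placebo variance would reduce the upper end. The GMR changes of 1.5% to 10.8% also assume a log-SD of 0.10 to 0.30 and perfect agreement between laboratories. An exclusion unrelated to response has no expected shift. Followed as written, this small estimation study of a single supervised infusion gives sound aPTT estimates.
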